10.3 Database management and quality control

The CRO working on behalf of Novartis will review the data entered into the CRFs by investigational staff for completeness and accuracy and instruct the site personnel to make any required corrections or additions. Queries are sent to the investigational site using an electronic data query. Designated investigator site staff is required to respond to the query and confirm or correct the data. If the electronic query system is not used, a paper Data Query Form will be faxed to the site. Site personnel will complete and sign the faxed copy and fax it back to the CRO working on behalf of Novartis who will make the correction to the database. The signed copy of the Data Query Form is kept at the investigator site.

Concomitant medications entered into the database will be coded using the WHO Drug Reference List, which employs the Anatomical Therapeutic Chemical classification system. Medical history/current medical conditions and adverse events will be coded using the Medical dictionary for regulatory activities (MedDRA) terminology.

Laboratory samples will be processed centrally and the results will be sent electronically to Novartis (or a designated CRO).

Randomization codes and data about all study drug(s) dispensed to the subject and all dosage changes will be tracked using an Interactive Response Technology (IRT). The system will be supplied by a vendor, who will also manage the database. The database will be sent electronically to Novartis (or a designated CRO).

Each occurrence of a code break via IRT will be reported to the clinical team and monitor. The code break functionality will remain available until study shut down or upon request of Novartis.

The occurrence of relevant protocol deviations will be determined. After these actions have been completed and the database has been declared to be complete and accurate, it will be locked and the treatment codes will be unblinded and made available for data analysis. Any changes to the database after that time can only be made after written agreement by Novartis management.

Commercially Confidential Information

10.4 Data Monitoring Committee

The study will be using a Data Monitoring Committee (DMC). A DMC is a group of professionals, experienced in clinical care and/or clinical research, assembled to provide additional safety oversight to a clinical study. The DMC will operate in accordance with a DMC charter which will be completed prior to FPFV. The DMC will meet on a regular basis to review trial safety data; and the DMC will meet on an *ad-hoc* basis to review individual SAEs. Additional information can be found about the DMC in [Section 7.5](#).

10.5 Adjudication Committee

The study will be using an Adjudication Committee. The committee will be reviewing a subset of SAE(s), in a blinded fashion, in order to confirm the diagnosis of acute exacerbation of IPF and, if necessary, determine the cause of any deaths (these are efficacy endpoints). The Adjudication Committee will have a charter completed prior to FPFV.

11 Data analysis

The primary efficacy and safety analysis will occur when the last randomized patient completes the treatment epoch unless the study is stopped for futility or early efficacy at the interim analysis, in which case the interim analysis will be called the primary efficacy and safety analysis.

Commercially Confidential Information

Any data analysis carried out independently by the investigator should be submitted to Novartis before publication or presentation.

11.1 Analysis sets

For all analysis sets, subjects will be analyzed according to the study treatment(s) received.

The safety analysis set will include all subjects that received any study drug.

The PD analysis set will include all subjects with available PD data and no protocol deviations with relevant impact on PD data.

The PK analysis set will include all subjects with at least one available valid (i.e. not flagged for exclusion) PK concentration measurement who received any study drug and with no protocol deviations that impact on PK data.

The IG analysis set will include all subjects with at least one available valid (i.e. not flagged for exclusion) IG concentration measurement, who received any study drug and with no protocol deviations that impact on IG data.

11.2 Subject demographics and other baseline characteristics

All data for background and demographic variables will be listed by treatment group and subject. Summary statistics will be provided by treatment group.

Relevant medical history, current medical conditions, results of laboratory screens, drug tests and any other relevant information will be listed by treatment group and subject.

11.3 Treatments

Data for study drug administration (rescue medication) and concomitant therapies will be listed by treatment group and subject.

11.4 Analysis of the primary variable(s)

The primary objective of the study is to assess the efficacy of VAY736 on top of current standard-of-care therapy (pirfenidone, nintedanib, or no IPF-specific treatment) using FVC (ml) at the end of treatment epoch (48 weeks of treatment) in patients with idiopathic pulmonary fibrosis.

11.4.1 Primary Variable(s)

The primary efficacy endpoint is the change from baseline in FVC (ml).

11.4.2 Statistical model, hypothesis, and method of analysis

The following hypothesis will be tested for VAY736+SoC versus placebo+SoC:

H_0 : There is no difference or worsening in change from baseline in FVC (ml) from baseline to 48 weeks of treatment between VAY736+SoC and placebo+SoC

H_1 : There is an improvement in change from baseline in FVC (ml) from baseline to 48 weeks of treatment between VAY736+SoC and placebo+SoC

Test will be conducted at a one-sided 10% level and 2-sided 80% CI of the estimates will be displayed.

The primary variable, change from baseline in FVC (ml), after 48 weeks of treatment will be analyzed using Mixed Effects Model for Repeated Measures (MMRM). The model will include treatment and visit as fixed effects, standard of care treatment (Nintedanib, Pirfenidone, neither) as factor and baseline value as a covariate, treatment-by-visit and baseline-by-visit as interaction terms. The patient effect will be assumed to be random and unstructured covariance matrix will be assumed for within-patient variation. The main comparison will be a contrast between treatment groups at 48 weeks of treatment. This approach assumes data is Missing At Random (MAR).

Summary statistics of change from baseline in FVC by epoch and treatment will be presented.

11.4.3 Handling of missing values/censoring/discontinuations

Given the severity of disease and the likelihood of some missing data, this study will also include approaches to assess treatment under the assumption of missing not at random.

11.4.4 Sensitivity analyses

A sensitivity analysis that uses alternative approaches to missing data will also be evaluated.

11.5 Analysis of secondary variable(s)

11.5.1 Efficacy / Pharmacodynamics

Survival analysis

At the end of the treatment epoch, the Kaplan-Meier estimates of the proportion of patients with the event of interest, along with 80% two-sided confidence intervals using Greenwood's formula, will be provided. In addition, the Kaplan-Meier estimates will be plotted against time.

The two treatment groups will be compared using a one-sided logrank test at the 10% significance level. The hazard ratio and its associated 80% two-sided confidence intervals will be estimated.

Event of interest is defined as:

1. All-cause mortality
2. IPF-related mortality

Progression-free survival (PFS) analysis

Same survival analysis as defined above will be produced at the end of the treatment epoch for the following event of interest:

1. Events, defined as: death (all-cause mortality) **OR** "progression" (relative reduction in FVC $\geq 10\%$)
2. Events, defined as: death (IPF-related mortality) **OR** "progression" (relative reduction in FVC $\geq 10\%$)

Disease progression

At the end of the treatment epoch, the Kaplan-Meier estimates of the proportion of patients with progression, along with 80% two-sided confidence intervals using Greenwood's formula, will be provided. The two treatment groups will be compared using a one-sided logrank test at the 10% significance level. The hazard ratio and its associated 80% two-sided confidence intervals will be estimated.

1. Progression, defined as: relative reduction in FVC $\geq 10\%$
2. Progression, defined as: relative reduction in DLcO $\geq 15\%$
3. Progression, defined as: absolute reduction in 6MWD ≥ 50 m

Composite endpoint

At the end of the treatment epoch, the Kaplan-Meier estimates of the proportion of patients with event of interest, along with 80% two-sided confidence intervals using Greenwood's formula, will be provided, where events of interest is defined as below. The two treatment groups will be compared using a one-sided logrank test at the 10% significance level. The hazard ratio and its associated 80% two-sided confidence intervals will be estimated.

1. death (all-cause mortality), **OR** relative reduction in FVC $\geq 10\%$, **OR** relative reduction in DLcO $\geq 15\%$, **OR** relative reduction in 6MWD ≥ 50 m
2. death (IPF-related mortality), **OR** relative reduction in FVC $\geq 10\%$, **OR** relative reduction in DLcO $\geq 15\%$, **OR** relative reduction in 6MWD ≥ 50 m

Pulmonary physiology

Change from baseline to the end of treatment epoch in DLCO will be analyzed by fitting the same model as described for the primary endpoint above in addition to summary statistics by treatment.

Exercise capacity

Change from baseline to the end of treatment epoch in 6-minute walk distance and in distance-saturation product will be analyzed by fitting the same model as described for the primary endpoint above in addition to summary statistics by treatment.

Gas exchange

Change from baseline to the end of treatment epoch in resting oxygen saturation (on room air) will be analyzed by fitting the same model as described for the primary endpoint above in addition to summary statistics by treatment.

Commercially Confidential Information

11.5.2 Safety

Vital signs

All vital signs data will be listed by treatment group, subject, and epoch/visit/time and if ranges are available abnormalities (and relevant orthostatic changes) will be flagged. Summary statistics will be provided by epoch, treatment and visit/time.

ECG evaluations

All ECG data will be listed by treatment group, subject and epoch/visit/time, abnormalities will be flagged. Summary statistics will be provided by epoch, treatment and visit/time.

Clinical laboratory evaluations

All laboratory data will be listed by treatment group, subject, and epoch/visit/time and if normal ranges are available abnormalities will be flagged. Summary statistics will be provided by epoch, treatment and visit/time.

Adverse events

All information obtained on adverse events will be displayed by treatment group, epoch and subject.

The number and percentage of subjects with treatment-emergent adverse events will be tabulated by body system and preferred term with a breakdown by treatment. A subject with multiple treatment-emergent adverse events within a body system is only counted once towards the total of this body system.

A treatment-emergent adverse event is defined as any adverse event that develops on or after the time of the first drug intake or any event already present that worsens following exposure to the study treatment.

All adverse events will be listed.

11.5.3 Pharmacokinetics

Commercially Confidential Information

Commercially Confidential Information

11.5.4 Pharmacokinetic / pharmacodynamic interactions

Commercially Confidential Information

11.5.5 Other assessments

Immunogenicity

Commercially Confidential Information

11.6 Analysis of exploratory variables

Commercially Confidential Information

Commercially Confidential Information

Commercially Confidential Information

11.7 Sample size calculation

In total 58 subjects are going to be randomized to the study in a 1:1 randomization. Assuming a treatment period of 48 weeks with 2 arms, VAY736+Standard-of-Care (SoC) vs. Placebo+SoC, and standard deviation of 250 ml for FVC (ml); a total sample size of 58 patients with 48 weeks data will give at least 80% power to detect a treatment improvement in change from baseline in FVC (ml) between VAY736+SoC and Placebo+SoC of 160ml in patients with Idiopathic Pulmonary Fibrosis (IPF).

The sample size calculation is based on the primary efficacy endpoint of change from baseline in FVC (ml) at week 48. The criteria for this calculation aimed for a 90% level of proof that difference in change in FVC from baseline to week 48 between VAY736+SoC and placebo+SoC > 0 and the mean treatment+SoC effect is at least 110 ml better than placebo+SoC effect. The former targets proof that the treatment+SoC produces a statistically significant improvement in change from baseline in FVC, while the latter targets proof of clinical relevance.

Commercially Confidential Information

The overall type I error at the end of study will be approximately 12% under this sample size.

If more than 20% of the randomized patients have not completed the 48 weeks of treatment, per protocol, then patients may be replaced.

R software version 3.0.3 ([Fisch et 2015](#)) was used.

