23. Historical (within 6 months prior to screening) treatment for IPF with experimental or off-label modalities including but not limited to oral corticosteroids, N-Acetylcysteine, cyclophosphamide, mycophenolate, azathioprine, cyclosporine A, etanercept, or plasmapheresis.
 - a. Treatment for any indication with any of the following drugs within 6 months prior to screening: oral corticosteroids, N-Acetylcysteine, cyclophosphamide, mycophenolate, azathioprine, cyclosporine A, etanercept, or plasmapheresis. (Note: The aforementioned treatments are systemically distributed and, therefore, might potentially affect the lung regardless of target indication).
24. Prior use of any B-cell depleting therapy (e.g., rituximab, ofatumumab, or other anti-CD20 mAb, anti-CD40, anti-CD19, anti-CD22 mAb, anti-CD52 mAb, or anti-BAFF mAb)
25. Receiving any treatment for pulmonary hypertension OR treatment for pulmonary hypertension anticipated during this trial (in other words, treatment for pulmonary hypertension is prohibited during this trial), including but not limited to epoprostanil, iloprost, treprostilan, selexipag, bosentan, ambrisentan, macitentan, sildenafil, tadalafil, and riociguat.
26. History of alcohol and/or drug abuse within the last 2 years
27. Elective surgery planned to take place during this trial

Commercially Confidential Information

A total of approximately 58 patients will be enrolled in the study and randomized. If more than 20% of the randomized patients have not completed the 48 weeks of treatment, per protocol, then patients may be replaced.

The investigator must ensure that all subjects being considered for the study meet the above eligibility criteria. No additional criteria should be applied by the investigator, in order that the study population will be representative of all eligible subjects.

Subject selection is to be established by checking through all eligibility criteria at screening. A relevant record (e.g. checklist) of the eligibility criteria must be stored with the source documentation at the study site.

Deviation from **any** entry criterion excludes a subject from enrollment into the study.

No additional exclusions may be applied by the investigator, in order to ensure that the study population will be representative of all eligible patients.

5 Restrictions for Study Subjects

For the duration of the study, the subjects should be informed and reminded of the restrictions outlined in this section.

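### Do the stated 80% power, 10% test level and 12% overall type I error in section 11.7 fail to belong to one design?

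*Protocol*

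**What the plan says.** Protocol section 11.7 fixes the size: "In total 58 subjects are going to be randomized to the study in a 1:1 randomization". With SD 250 mL it claims that "a total sample size of 58 patients with 48 weeks data will give at least 80% power" to detect a 160 mL improvement. The next paragraph says that the calculation aimed at two things: a 90% level of proof that the difference exceeds zero, and that "the mean treatment+SoC effect is at least 110 ml better than placebo+SoC effect". A blacked-out block follows, and then: "The overall type I error at the end of study will be approximately 12% under this sample size".

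Section 11.4.2 says of the primary hypothesis: "Test will be conducted at a one-sided 10% level and 2-sided 80% CI of the estimates will be displayed". SAP section 6.1.3 repeats this.

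The opening of protocol section 11 (Data analysis) times the primary analysis at completion of the treatment epoch by the last randomized patient, "unless the study is stopped for futility or early efficacy at the interim analysis". In that case the interim analysis becomes the primary one. The timing and rule of the interim (protocol sections 3.5 and 11.9, SAP section 3) are blacked out.

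On attrition, sections 4.2 and 11.7 both say: "If more than 20% of the randomized patients have not completed the 48 weeks of treatment, per protocol, then patients may be replaced".

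**The concern.** Three readings of section 11.7 invite doubt.

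- **Power.** With 29 patients per arm, a result is significant at one-sided 10% once the estimate passes about 84 mL. The 110 mL criterion is stricter, so it decides success, and a single final look then falls short of 80%.
- **Level.** A 10% test stands next to a 12% overall error, and one of the two seems wrong.
- **Completers.** The power sentence needs 58 patients with 48-week data. Only 58 are randomized, and replacement is optional and starts only after more than 20% have not completed.

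If these were real contradictions, whoever takes the go/no-go decision would be relying on a power or an error rate that the rule does not have.

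**Working it through.** **Inputs.** From protocol section 11.7: 29 per arm, SD 250 mL, true difference 160 mL, second criterion 110 mL (read as a point estimate of at least 110 mL). From section 11.4.2: one-sided 10%, so z = 1.2816.

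**1. The quoted power on its own inputs.**

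SE = 250 × √(2/29) = 65.65 mL.

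Power = Φ(160/65.65 − 1.2816) = Φ(1.155) = 87.6%. With the noncentral t on 56 degrees of freedom it is 87.2%. At least 80% is true.

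**2. Two-part rule, final look only.**

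- Significance cut: 1.2816 × 65.65 = 84.1 mL, so 110 mL binds.
- Power: Φ((160 − 110)/65.65) = Φ(0.762) = 77.7%.
- Type I error: 1 − Φ(110/65.65) = 4.7%.

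This is the combination that misses 80%. It also cannot produce an overall error of 12%, and neither can significance alone at one look, which gives 10%. The 12% must therefore cover more than one look, which agrees with the early-efficacy interim in section 11.

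**3. Two-part rule at an interim and again at the end.** The timing is not readable, so I assume an information fraction f and show a range. There is no futility stop in this calculation. At the interim SE₁ = 65.65/√f, and the cut is the larger of 110 mL and 1.2816 × SE₁. At f = 0.5, SE₁ = 92.85 mL and the cut is 119.0 mL. The two estimates are bivariate normal with correlation √f, and success means passing the cut at either look.

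| Information fraction | Overall type I error | Power at 160 mL |
|---|---|---|
| 0.3 | 12.6% | 82.6% |
| 0.4 | 12.3% | 83.1% |
| 0.5 | 11.9% | 83.5% |
| 0.6 | 11.2% | 83.8% |
| 0.7 | 9.4% | 83.1% |

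From 0.3 to 0.6 the error is close to 12%, and power exceeds 80% throughout. A futility stop would lower both figures somewhat.

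**4. 10% against 12%.** Section 11.4.2 gives the level at which the test is done. Section 11.7 gives the overall error at the end of the study. At f = 0.5 in step 3, the first look alone has a 10% error (the cut of 119.0 mL is exactly 1.2816 × 92.85), and the two looks together have 11.9%. Both numbers describe the same procedure.

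**5. Attrition.** A loss of 20% from 58 leaves 58 × 0.8 = 46.4, so take 46, or 23 per arm.

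- SE = 250 × √(2/23) = 73.72 mL.
- Significance alone: 80.7% (noncentral t, 44 degrees of freedom).
- Two-part rule, final look only: Φ(50/73.72) = 75.1%.
- Two-part rule at two looks, f = 0.5: power 80.2%. For f from 0.3 to 0.7 it is 79.7% to 80.6%.

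This is a worst case. The 20% counts patients who do not complete treatment per protocol, which is not the same as lacking a week-48 FVC. Section 7.2 keeps patients who stop treatment in follow-up and encourages them to attend the scheduled visits for spirometry, and the MMRM uses whatever visits exist.

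**The case for a change.** The strongest opposing case is about what the readable text lets a reader conclude. Section 11.7 names both success criteria, yet does not say which of them, or which looks, the 80% covers. Depending on the reading, power is 87%, 78% or about 84%, and the error is 10%, 4.7% or 12%. Sections 11.4.2 and SAP 6.1.3 state only 10%. If 46 patients supply data, the two-look illustration gives power of only about 80% and, at half information, a type I error of 13.1%. An unadjusted 80% interval after an efficacy look also covers less than 80% near the null: 74.8% at zero effect in the half-information illustration.

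The arithmetic stands, and so does the remark that the readable text leaves the labels implicit. The step from there to an error does not. A blacked-out block lies between the two criteria and the 12% sentence, and the interim sections are blacked out too. The missing labels, or an adjustment of the interval, may be there, and text removed for confidentiality is not missing from the plan. The 13.1% and the coverage figure belong to an assumed interim, and the 13.1% also needs the worst-case completer count. The 12% is disclosed in section 11.7, not hidden behind the 10%. Section 3.1 calls the trial exploratory and non-confirmatory, and nothing in the documents requires the overall error to equal 10%.

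**Conclusion.** The concern does not hold. The power statement is true on its own inputs (87.2% for significance alone). It is also true under the two-part rule once the early-efficacy interim is counted: 83.5% at half information, and 82.6% to 83.8% over fractions 0.3 to 0.7. The same reconstruction yields an overall type I error of 11.9%, in line with the stated 12%. The 77.7% and 4.7% describe a single-look design, which is not this trial's. The 10% and the 12% are a per-test level and an overall error. The 46-patient case is a lower bound on information, and even there power is 80.7% for significance alone and 80.2% for the two-look rule.

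This rests on an assumed interim: one look, the same two-part rule as at the end, 110 mL read as a point estimate, and no futility stop. The documents cannot confirm that design. It is enough, though, to show that the stated figures are compatible, and therefore that no error has been demonstrated. Replacing them with final-look-only figures, or with an interim boundary tuned to a guessed timing, would put numbers into the plan that the documents do not support.

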11.8 Power for analysis of key secondary variables

Not applicable

11.9 Interim analyses

Commercially Confidential Information

12 Ethical considerations

12.1 Regulatory and ethical compliance

This clinical study was designed and shall be implemented, executed and reported in accordance with the ICH Harmonized Tripartite Guidelines for Good Clinical Practice, with applicable local regulations (including European Directive 2001/20/EC, US Code of Federal Regulations Title 21, and Japanese Ministry of Health, Labor, and Welfare), and with the ethical principles laid down in the Declaration of Helsinki.

